## **Abbreviations**

ACO, acute coronary occlusion

CABG, Coronary artery by-pass grafting

ECG, electrocardiogram

LVEF, left ventricular ejection fraction

MI, myocardial infarction

NSTEMI, non-ST-segment elevation myocardial infarction

PCI, percutaneous coronary intervention

STE, ST-segment elevation

STEMI, ST-segment elevation myocardial infarction

## Study Project Summary

The underlying conceptual flow of the study as follows:

- Universally recommended STEMI criteria come from the studies designed for discriminating biomarker-positive MI (mainly CK-MB) from benign-variant STE.
- In these studies, neither coronary angiography had been utilized nor acute coronary occlusion (ACO) had been sought for.
- Now, the term STEMI is used synonymously with ACO.
- However, it restricts our thinking to the point that it is only the ST-segment that matters for the reperfusion decision, there is no need for taking any other ECG variable into account, such as preceding QRS-complex, following T-wave or even the morphology of ST-segment itself.
- Recent studies clearly indicated that any STE should be interpreted in context of other ECG variables. Some ACO localizations may not show STE in contiguous leads and some may not show any STE at all (hyperacute T-waves, DeWinter's pattern etc.).
- In reality, STEMI criteria have a limited diagnostic accuracy for ACO, causing a substantial amount of false catheterization laboratory activations.
- More importantly, they miss nearly one-third of ACO and causing this unfortunate group of patients, labeled as non-STEMI, to be deprived of emergent reperfusion therapy, as in the old days of Q-wave/non-Q-wave MI approach.
- Additionally, the term STEMI is somewhat self-contradictory, since a patient without STE on ECG, but ACO on angiogram, still classified as non-STEMI. But ACO-MI/non-ACO-MI terminology is not limited by ECG signs and permits retrospective reclassification of these patients.

- Several authors called for a new paradigm shift from STEMI/non-STEMI to ACO-MI/non-ACO-MI, as ACO can be reliably recognized with the help of many other ECG findings, however, it is uncertain whether this new approach would result in better identification of the patients who need acute reperfusion therapy and/or ECG has sufficient diagnostic power to go beyond established STEMI criteria.
- The objective of this study is to provide answers to these critical questions.

## **Study General Procedures**

### **1. Application for Institutional Review Board (IRB)/Ethics board approval**

IRB/Ethics board approval will be obtained from [name] Thoracic and Cardiovascular Surgery Training and Research Hospital.

### **2. Patient selection**

We planned to enroll 1000 patients in each of the STEMI, NSTEMI and control groups.

Considering [name] Thoracic and Cardiovascular Surgery Training and Research Hospital has a large local network for primary with around 1000-1500 STEMI patients per year referred for primary PCI, it will take approximately one-year period to collect 1000 STEMI patients. This institution also receives STEMI and NSTEMI patients with a 2:1 ratio, which corresponds well to the reported incidences of these two entities. Therefore, we expected to enroll 1000 NSTEMI patients before STEMI group is completed. Another 1000 patients with a clinical picture compatible with an acute coronary event, but without any ECG changes during serial follow-up and negative and unchanging troponin levels within the first 24 hours will be enrolled. As these patients were so much in frequency, and this group would be completed at the beginning of the study, if we started at the same time with

STEMI/NSTEMI enrollment (May 1, 2017); we decided to select these patients from a computer-generated random list. Therefore, the patients in these group was enrolled after first two groups were completed (December 31, 2018). The total admission counts will also be calculated for the weighted analysis of diagnostic accuracy indexes; such as sensitivity, specificity, negative and positive predictive value. After this enrollment period we will have three cohorts.

- STEMI group: These patients should have all of the following criteria: (1) New ST-segment elevation at the J-point in two contiguous leads with the cut-point:  $\geq 1$  mm in all leads other than leads V2–V3 where the following cut-points apply:  $\geq 2$  mm in men  $\geq 40$  years;  $\geq 2.5$  mm in men  $< 40$  years, or  $\geq 1.5$  mm in women regardless of age. (2) a peak troponin level above 99th percentile and (3) a clinical picture compatible with acute coronary syndrome.
- NSTEMI group: These patients should have both of the following criteria: (1) a peak troponin level above 99th percentile and (2) a clinical picture compatible with acute coronary syndrome. But these patients should not have STEMI criteria ((1) New ST-segment elevation at the J-point in two contiguous leads with the cut-point:  $\geq 1$  mm in all leads other than leads V2–V3 where the following cut-points apply:  $\geq 2$ mm in men  $\geq 40$  years;  $\geq 2.5$  mm in men  $< 40$  years, or  $\geq 1.5$  mm in women regardless of age).
- Control group: These patients should have (1) a technically adequate ECG, (2) a clinical picture compatible with acute coronary syndrome, (3) a peak troponin level below 99th percentile or, if low-positive, change in the first 12-hours should

be less than 20%.

All of these patients may or may not have undergone catheterization during their hospital stay.

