### **4. Data Collection**

- 1) Starting from May 1, 2017 hospital database will be screened for STEMI and NSTEMI admissions.
- 2) Following will be checked:
  - The presence of a technically adequate (pre-cath) ECG.
  - A peak troponin level over 99 th percentile.
- 3) ECGs will be printed and handed over to ECG reviewers after all groups are completed.
- 4) Following baseline variables will be entered to the study Excel spreadsheet:  
Enrollment no., protocol no., cohort, age, gender, prior history of MI, prior history of PCI or CABG, presence or absence of diabetes (medication use or HbA1c>6.5), hypertension (medication use or average blood pressure over 140/90 mmHg during hospital stay), dyslipidemia (medication use), smoking (current smoker or past smoker with in 1 year), admission systolic blood pressure, admission heart rate, admission creatinine level, admission hemoglobin level, Killip class on admission, admission troponin I level (from a blood sample collected before, during or just after coronary angiography or at admission to the emergency department), peak troponin level (the maximum troponin level during hospital stay), 24-to-48 hour troponin level (the highest troponin level during this time window), ejection fraction from echocardiogram report, time from ECG to PCI (will be calculated from system recordings), in-hospital mortality, in-hospital resuscitation, in-hospital intubation.
- 5) From these parameters, baseline GRACE risk score, the change within troponin value in the first 24 hours will be calculated.

- 6) Angiograms will be reviewed by angiogram reviewers from hospital digital database. Following points will be noted: (1) the presence of total occlusion. The presence of collaterals to distal vessel, appearance of the total occlusion, easiness of guidewire crossing will also be assessed to determine if the total occlusion is acute in nature. If necessary, primary operator will also be contacted. (2) The presence of culprit lesion, which was defined based on several angiographic properties including appearance, presence of angiographic thrombus, critical stenosis with less than Thrombolysis in Myocardial Infarction 3 flow.

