### **ECG Interpretation**

1. **Type 1 EGGs:** New ST-segment elevation at the J-point in two contiguous leads with the cut-point:  $\geq 1$  mm in all leads other than leads V2–V3 where the following cut-points apply:  $\geq 2$ mm in men  $\geq 40$  years;  $\geq 2.5$  mm in men  $< 40$  years, or  $\geq 1.5$  mm in women regardless of age.
  - a. **Type 1a:** The amplitude, morphology, extent of STE and the presence of additional findings (hyperacute T waves, Q-waves, terminal QRS distortion) make ECG highly obvious for MI presumably due to acute, thrombotic occlusion. These ECGs will be included in both STEMI and ACO-MI groups.
  - b. **Type 1b:** Does not meet recommended criteria for STEMI, but highly suggestive for MI, despite being subtle and difficult. Possible findings are minor STE with minor reciprocal ST-depression not fulfilling STEMI criteria, hyperacute T-waves or DeWinter's pattern, subtle anterior STE hard to differentiate from benign variant STE and nonconsecutive STE. These ECGs will be included in ACO-MI group but not in STEMI group.
  - c. **Type 1c:** There is ST-segment elevation that meets criteria for STEMI, but it is

uncertain whether it is due to MI or to another condition, such as benign variant STE, left ventricular hypertrophy, left bundle branch block, prior MI, pericarditis, etc. These ECGs will be included in STEMI group but not in ACO-MI group, unless there are additional findings suspicious for acute coronary occlusion as follows:

- i. Differential diagnosis for benign variant STE: Type 1c, if fulfills STEMI criteria. But re-classified as Type 1b, if Aslanger's formula is positive.
  - Aslanger's formula:  $(R\text{-wave amplitude in lead V4} + QRS \text{ amplitude in V2}) - (QT \text{ interval in millimeters} + STE_{60} \text{ in V3}) < 12$
  - *Reference:* Aslanger E, Yıldırım Türk Ö, Bozbeyoğlu E, et al. A Simplified Formula Discriminating Subtle Anterior Wall Myocardial Infarction from Normal Variant ST-Segment Elevation. *Am J Cardiol* 2018; 122: 1303-9.
- ii. Differential diagnosis for left ventricular hypertrophy
  - Type 1c unless ST segment to R-S-wave magnitude is equal or greater than 25% (then indicates ACO, Type 1b).
  - *Reference:* Armstrong EJ, Kulkarni AR, Bhave PD, et al. Electrocardiographic criteria for ST-elevation myocardial infarction in patients with left ventricular hypertrophy. *Am J Cardiol* 2012; 110: 977-83.
- iii. Differential diagnosis for isolated left bundle branch block:

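### Section 2 gives two different control-group rules; if the narrative rule was applied, troponin-negative patients with changing ECGs fall in no cohort, and specificity and PPV do not describe the admitted population.

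*Combined protocol and SAP*

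**What the plan says.** All three cohorts are defined in section 2, Patient selection.

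- **Narrative rule for controls.** Compatible clinical picture, "but without any ECG changes during serial follow-up and negative and unchanging troponin levels within the first 24 hours will be enrolled". The same paragraph explains how controls were drawn: "we decided to select these patients from a computer-generated random list". On timing it adds that "the patients in these group was enrolled after first two groups were completed".
- **Cohort-list rule for controls.** A technically adequate ECG, a compatible clinical picture, and a peak troponin below the 99th "percentile or, if low-positive, change in the first 12-hours should" stay under 20%. No number defines low-positive.
- **MI cohorts.** Both require raised troponin. For NSTEMI: "These patients should have both of the following criteria: (1) a peak troponin level above" the 99th percentile. The STEMI entry has the same troponin requirement in addition to ST elevation. The database screen in section 4 (Data Collection) repeats it: "A peak troponin level over 99 th percentile".
- **Use of the cohorts.** Section 2 announces a "weighted analysis of diagnostic accuracy indexes; such as sensitivity, specificity, negative and positive predictive value". The Statistical Analysis section plans sensitivity, specificity and accuracy for both ECG approaches, then a repeat weighted to total admissions.

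**The concern.** The two control rules differ on the ECG condition (present or absent), on troponin (negative only, or low-positive allowed) and on the window (24 or 12 hours). The ECG condition matters most, because the ECG is the test being evaluated. Under the narrative rule, controls are selected on serial ECG change, which is closely related to the index test.

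Controls carry much of the information on specificity. ACO Adjudication requires a troponin I of at least 1.0 ng/ml with a rise, a peak above 5.0 ng/mL, or a cardiac arrest, so controls will be almost entirely non-ACO. The Study Project Summary makes false catheterization laboratory activation part of the rationale, so specificity and PPV bear directly on the study question. A patient type that no cohort samples cannot be recovered by weighting the cohorts.

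**Working it through.** **Step 1: which cohort takes which patient?** A compatible clinical picture is assumed throughout.

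| Patient | STEMI / NSTEMI | Control, narrative | Control, list |
|---|---|---|---|
| Troponin-negative, changing ST elevation | no (troponin) | no (ECG) | yes |
| Troponin-negative, other serial ECG change | no (troponin) | no (ECG) | yes |
| Troponin-negative, fixed ST elevation | no (troponin) | yes | yes |
| Low-positive, change under 20% | yes, if low-positive means above the 99th percentile | no | yes |

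Rows 1 and 2 are the gap under the narrative rule. Row 4 is an overlap under the list rule, with no stated precedence.

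**Step 2: size.** The plan has no figure to reproduce. Inputs:

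- From the documents: 1000 patients per cohort; STEMI to NSTEMI admissions 2:1 (section 2); 25% ACO-MI in non-STE-MI (sample-size section), used as a proxy for NSTEMI.
- Assumed: ACO in 85% of STEMI and 0% of controls; control admission weight 1, 3 or 10; STEMI-criteria ST elevation in f = 1% to 15% of troponin-negative patients; a share d = 5% or 20% of these lost for serial change.

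Control share of non-ACO patients: s = W3 / (0.15·W1 + 0.75·W2 + W3).
- 1:1:1: 1/1.90 = 0.526
- 2:1:3: 3/4.05 = 0.741
- 2:1:10: 10/11.05 = 0.905

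Let L be the share of all controls lost who are STEMI-negative. The remaining ST-elevation share is f′ = f(1 − d)/(1 − f·d − L), and STEMI specificity shifts by s(f − f′). The shift is positive only if d exceeds the proportion lost among STEMI-negative controls, L/(1 − f).

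Example with f = 15%, d = 20%, L = 0: f′ = 0.12/0.97 = 0.1237. The shift is 0.526 × 2.63 = 1.38 points, or 0.905 × 2.63 = 2.38 points.

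Now suppose Type 2 ECGs occur in 10% of controls and half are lost (L = 0.05). At f = 5% the break-even d is 0.05/0.95 = 5.3%, just above d = 5%.

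| Shift in STEMI specificity (points) | 1:1:1 | 2:1:10 |
|---|---|---|
| f = 5%, d = 5%, L = 0 | +0.13 | +0.22 |
| f = 5%, d = 5%, L = 0.05 | −0.01 | −0.01 |
| f = 15%, d = 5%, L = 0 | +0.34 | +0.58 |
| f = 15%, d = 5%, L = 0.05 | −0.06 | −0.11 |
| f = 15%, d = 20%, L = 0 | +1.38 | +2.38 |
| f = 15%, d = 20%, L = 0.05 | +1.03 | +1.77 |

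At 2:1:3 the f = 15%, d = 20%, L = 0 figure is +1.95. Also losing half of a 3% Type 1b share (L = 0.065) takes the f = 15%, d = 5% row to −0.19 and −0.33.

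**Step 3: against sampling error.** Unweighted, there are 150 + 750 + 1000 = 1900 non-ACO patients, and specificity is 1 − (150 + 1000f)/1900. The 95% half-width is 1.96·√(spec(1 − spec)/1900).
- f = 1%: spec 0.916, half-width 1.2 points
- f = 5%: spec 0.895, half-width 1.4 points
- f = 15%: spec 0.842, half-width 1.6 points

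The unweighted shift stays below its own half-width at each f (at f = 15%, 1.38 against 1.64).

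**Step 4: PPV at 2:1:10.** PPV = 1.7/(1.7 + 0.3 + 10f′). At f = 15% with no loss it is 1.7/3.5 = 48.6%. With d = 20% and L = 0 it is 1.7/3.237 = 52.5%. With d = 5% and L = 0.065, f′ = 0.1425/0.9275 = 0.1536 and PPV is 1.7/3.536 = 48.1%. The shift therefore runs from about −0.5 to +3.9 points.

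**Step 5: ACO approach minus STEMI criteria.** Type 1c/1d ECGs (share c) are positive on STEMI criteria only. Of Type 1b (share b) the ECG Interpretation section says "These ECGs will be included in ACO-MI group but not in STEMI group". With losses dc and db and remaining fraction D, the bias is s·{[c(1 − dc) − b(1 − db)]/D − (c − b)}.
- c = 5%, dc = 20%, b = 0: −0.5 (1:1:1), −0.9 (2:1:10)
- c = b = 5%, both losses 20%: 0
- c = 5%, dc = 5%, b = 3%, db = 50%: +0.7, +1.2
- the same with half of a 10% Type 2 share lost: +0.8, +1.3

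**The case against.** The best defence is that the cohort list is the formal criteria statement and the narrative is a remark on feasibility. The narrative itself leads into the list, and section 4 sends ECGs to the readers only once all groups are complete, so study ECG types were not available when controls were chosen. This has force: the list may well be the rule applied, and then the ECG bias is zero. It does not settle the matter. The random-list sentence is in the narrative and refers back to the patients described there. A section between the sample-size text and section 4 was not available and could contain a clarification.

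A reader might infer three stronger things that the documents do not support:

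- **That controls were chosen on the index test itself.** The classified test is a technically adequate pre-catheterization ECG. The narrative restricts serial change, which is related but different, and on its natural reading fixed ST elevation stays in.
- **That STEMI specificity must be overstated.** This requires ST-elevation patients to be lost more often than STEMI-negative ones. With plausible Type 2 losses, the small-d rows fall to zero or just below.
- **That the bias could reach 8 to 14 points.** With d = 100% and f = 15% the formula gives 7.9 (1:1:1) and 13.6 (2:1:10). That requires reading ECG changes as any abnormality, which the reference to serial follow-up does not favour.

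The mortality comparison within non-STE-MI is also not at issue, because controls are not in it.

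**Conclusion.** The inconsistency is certain and rests on no assumption. Its consequence is conditional. If the narrative rule was applied, troponin-negative patients with changing ECGs, including changing ST elevation, are in no cohort, and specificity and PPV, weighted or not, do not describe the admitted population.

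The size is unknown and probably modest. For serial change, the illustration gives a shift in STEMI specificity from about zero or slightly negative to 1.4 points unweighted, below the 1.2 to 1.6 point half-width at the matching f, and up to 2.4 points at 2:1:10. These figures depend on assumed values of f, d, the ECG-type shares, the ACO rate in STEMI and the control weight. The direction for the ACO-versus-STEMI comparison is not determined. The point should be corrected, with medium confidence that it affected the data. The troponin overlap is minor.

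**What to change.** 1. Delete the no-serial-ECG-change condition from the narrative, so that one definition governs, with no ECG requirement beyond technical adequacy.
2. Use one troponin rule and one time window in both places, with a numeric meaning for low-positive.
3. State which definition was applied when controls were drawn from the random list.
4. If it was the narrative rule, report how many listed patients were excluded for ECG changes, by ECG type. Then either add them to the controls, or state that specificity and PPV apply only to controls without serial ECG changes.
5. For low-positive, flat-troponin patients who meet both a control and an MI-cohort rule, state the precedence actually used and apply it to the admission weights. Do not reassign patients in the completed STEMI and NSTEMI cohorts: moving them out of NSTEMI would alter the population of the mortality comparison.

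**Cost.** If the list was applied, this is wording and a disclosure. If the narrative was applied, adding patients means re-screening the random list, with ECG reading, data entry and follow-up after data have been seen. The fallback costs only a narrower claim. Reported specificity may change, or its scope may shrink.

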### **ACO Adjudication**

Because the infarct-related artery may spontaneously open by the time of the angiogram or total occlusion may be chronic in nature, we defined a composite ACO using following criteria:

(1) total occlusion or presence of culprit lesion on angiography

PLUS

a peak troponin I level equal to or greater than 1.0 ng/ml

PLUS

at least 20% rise within 24 hours

(2) a highly elevated peak troponin, i.e., peak troponin I > 5.0 ng/mL, which was shown to be highly correlated with ACO

(3) cardiac arrest before any troponin rise has been documented with supporting clinical evidence of possible ACO.

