### **Statistical Analysis**

Baseline characteristics will be summarized using standard descriptive statistics. Comparisons of relevant parameters between groups will be performed by chi-square, Fisher's exact test, Mann-Whitney U, Kruskal-Wallis H test, one-way ANOVA and student t-test, as appropriate. Patients with missing values will be excluded pairwise from analyses. A Cohen's  $\kappa$  test will be used for determination of the intra- and inter-observer agreement for ECG classifications.

Kaplan-Meier analysis will be performed to determine the cumulative long-term mortality rates in different ECG subgroups. The mortality across groups will be compared using log-rank test. A Cox-regression model will be used to perform a survival analysis according to intervention timing and revascularization status. Baseline characteristics with a P value of 0.05 or less in the univariate analysis will be included and a step-down procedure will be applied for selection of final covariates.

**Note:** After data collection, we performed a univariate analysis for mortality and found that many of the baseline parameters, including age, systolic blood pressure, heart rate, baseline

creatinine etc., were significantly associated with long-term mortality. But when these were included in the Cox regression analysis alongside with baseline GRACE risk score, they all lost their statistical significance. Considering GRACE risk score already includes almost all of these variables, we only used GRACE risk score as a covariate in Cox regression model.

The sensitivity, specificity and diagnostic accuracy of STE/non-STE or ACO/non-ACO ECG approaches will be calculated using receiver operating characteristics analysis. As these parameters are highly dependent on the pre-test probability of the disease and pre-test probability of ACO and long-term mortality are closely associated with the presentation type, we will also repeat these analyses after weighing cases for the total number of hospital admissions in the study period.

Statistical analyses will be performed with SPSS (version 24.0; SPSS Inc., Chicago, IL) and MedCalc Software (version 18.2.1 [Evaluation version]; MedCalc Software, Ostend, Belgium).

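### The ACO reference standard cannot be fully applied to uncatheterised patients with peak troponin I of 1.0-5.0 ng/mL, and the plan has no rule for them, so the accuracy comparison may be distorted.

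*Combined protocol and SAP*

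**What the plan says.** The section 2. Patient selection closes its cohort definitions with: "All of these patients may or may not have undergone catheterization during their hospital stay". The same section describes the hospital as receiving "around 1000-1500 STEMI patients per year referred for primary PCI". It says nothing comparable about NSTEMI patients or controls.

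The section ACO Adjudication numbers three criteria. No connective is printed between them; because the definition is called a composite, they are read here as alternatives.

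- Criterion 1: "total occlusion or presence of culprit lesion on angiography", together with "a peak troponin I level equal to or greater than 1.0 ng/ml" and "at least 20% rise within 24 hours".
- Criterion 2: "a highly elevated peak troponin, i.e., peak troponin I > 5.0 ng/mL". No angiogram is needed.
- Criterion 3: "cardiac arrest before any troponin rise has been documented with supporting clinical evidence of possible ACO". No angiogram is needed.

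There is no indeterminate category and no rule for a patient without an angiogram. The only general provision is in Statistical Analysis: "Patients with missing values will be excluded pairwise from analyses". It does not say whether an absent angiogram is a missing value. The case weighting in that section is by total admissions, not by whether the reference standard could be applied. The baseline variable list in 4. Data Collection has no explicit item for catheterised yes or no.

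**The concern.** The study compares two readings of the ECG against adjudicated ACO. Whether criterion 1 can be assessed depends on catheterization, and catheterization may depend on the ECG: patients who meet STEMI criteria are sent for primary PCI. If so, this is partial verification linked to one of the index tests.

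A patient with true ACO, a peak in the 1.0-5.0 ng/mL band and no angiogram drops out of the ACO-positive class. If that happens mainly to patients without STEMI criteria, the ACO cases that STEMI criteria miss are undercounted and their sensitivity looks better than it is. The comparison with the ACO approach is affected too, because a Type 1b ECG is positive on that approach and negative on STEMI criteria. At stake is the accuracy comparison for ACO, for which the sample-size section takes an AUC difference of 0.07 (0.700 to 0.770).

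**Working it through.** **1. Which patients are affected.** For an uncatheterised patient:

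| Peak troponin I (ng/mL) | Criterion 1 | Criterion 2 | Effect of having no angiogram |
|---|---|---|---|
| below 1.0 | fails with or without an angiogram | fails | none |
| 1.0 to 5.0 | cannot be met | fails | ACO only through criterion 3 |
| above 5.0 | not needed | met | none |

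Within the band, only patients who truly had ACO and would have met all of criterion 1 are misclassified.

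**2. Inputs.** The plan states no expected sensitivity and no catheterization rate, so there is no figure of its own to reproduce here. From the documents: 1000 patients per cohort, and an ACO-MI frequency of 25% in NSTEMI, taken here as adjudicated ACO (itself an assumption). All else is assumed:

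- 85% ACO in the STEMI cohort and none in controls.
- The ACO approach detects 92% of ACO in the STEMI cohort and 60% in the NSTEMI cohort (as Type 1b).
- 20-50% of NSTEMI ACO cases peak at 1.0-5.0 ng/mL, and 10-50% of those are uncatheterised.
- Missed cases occur only in the NSTEMI cohort.

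**3. STEMI-criteria sensitivity.** True ACO = 850 + 250 = 1100. True sensitivity = 850/1100 = 77.3%.

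Missed cases m = 250 × share in band × share uncatheterised:

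- lowest: 250 × 0.20 × 0.10 = 5, giving 850/1095 = 77.6%
- highest: 250 × 0.50 × 0.50 = 62.5, giving 850/1037.5 = 81.9%

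This holds whatever the ECG type of the missed NSTEMI cases. It also holds if they are excluded instead of scored negative, since either way they leave the ACO-positive denominator; only specificity differs.

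**4. Equal loss.** With 20% of ACO cases missed in both cohorts, sensitivity = 680/880 = 77.3%. There is no inflation.

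**5. Sensitivity difference.** The ACO approach detects 0.92 × 850 + 0.60 × 250 = 782 + 150 = 932. True difference d = (932 − 850)/1100 = 0.0745. If a share s of the m missed cases is Type 1b, the observed difference is (82 − m·s)/(1100 − m), which is below d only if s > d. With m = 62.5:

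| s | Observed difference | Against 0.0745 |
|---|---|---|
| 0 | 82/1037.5 = 0.0790 | wider |
| 0.20 | 69.5/1037.5 = 0.0670 | narrower |
| 0.60 | 44.5/1037.5 = 0.0429 | narrower |

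The break-even share depends on the case mix. If instead all 850 STEMI-cohort ACO cases are positive on both approaches, d = 150/1100 = 0.136. With 50 missed cases the difference is then 0.143 at s = 0, 0.138 at 0.10, 0.133 at 0.20 and 0.114 at 0.60.

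**6. AUC difference.** For a two-level test, AUC = (sensitivity + specificity)/2. Non-ACO patients = 3000 − 1100 = 1900. STEMI criteria have 1000 − 850 = 150 false positives. The ACO approach needs a further assumed count. With 59 false positives, the true AUCs are (0.7727 + 0.9211)/2 = 0.8469 and (0.8473 + 0.9689)/2 = 0.9081, a difference of 0.061.

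Scoring 62.5 missed cases negative changes that difference to 0.063 at s = 0, 0.0535 at s = 0.20 and 0.035 at s = 0.60. With 40, 100 or 150 assumed false positives, the starting difference is 0.066, 0.050 or 0.037. The largest absolute loss stays at about 0.026 (0.025 at 150).

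**The case against.** The documents never say that these patients are scored negative; pairwise exclusion is an available reading. That stands as a point of wording. It does not remove the problem, because both readings give the same observed sensitivities.

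Differential verification is inferred from one phrase about primary PCI referral, and no catheterization rates are given. That also stands: with equal loss there is no inflation, so the overstatement must be put conditionally.

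A reader might infer that the bias necessarily works against the ACO approach and is therefore conservative, or that it removes some fixed proportion of the AUC difference. Neither is supported. Missed Type 2-4 cases are false negatives on both approaches and widen the gap slightly. Any proportional loss rests on an assumed Type 1b share and an assumed false-positive count, and the documents give neither.

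A reader might also infer that the NSTEMI mortality contrast is contaminated. That is not established. ECG Interpretation assigns patients to the ACO-MI group by ECG type, and Statistical Analysis plans survival curves by ECG subgroup. On that reading catheterization does not affect who is in the group. The mortality contrast is affected only if its ACO-MI subgroup is defined by adjudicated ACO, and the text leaves this open.

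Finally, the composite is deliberate, and criteria 2 and 3 do classify many patients without angiography. That narrows the gap to one troponin band but does not close it.

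**Conclusion.** The gap is real and follows from the text: optional catheterization combined with an angiogram-dependent criterion leaves ACO status incompletely ascertained at 1.0-5.0 ng/mL, and no rule covers it. Its size cannot be determined from the documents. Under the assumed rates, STEMI-criteria sensitivity rises from 77.3% to between 77.6% and 81.9%, provided missed ACO is proportionally more common without STEMI criteria. The difference between approaches is distorted. It probably shrinks if an appreciable share of the missed cases are Type 1b and widens slightly if almost none are. At the upper end the AUC difference could move by about 0.026, not negligible beside the planned 0.07; at the lower end the effect is trivial. This should be dealt with in the analysis plan. It does not undermine the design.

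**What to change.** 1. Record catheterised yes or no, and report it by cohort and ECG type.
2. In the accuracy analysis, class uncatheterised patients with peak troponin I of 1.0-5.0 ng/mL who do not meet criterion 3 as reference status unknown.
3. Report the comparison of sensitivity, specificity and AUC three ways: these patients taken as all negative, all positive, and excluded.
4. Optionally add multiple imputation or inverse-probability-of-verification weighting on ECG type, troponin and GRACE score. State that this assumes verification is explained by those variables; the all-negative and all-positive bounds do not need that assumption.
5. State whether the ACO-MI subgroup in the NSTEMI mortality contrast is defined by ECG type or by adjudicated ACO.

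The cost is some added wording and modest extra analysis, mostly on data already being collected. No patient has to be dropped from the study. Intervals become somewhat wider where the unknown group is excluded or imputed.
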